8 CONVENTIONS

See Core Safety SAP¹.

For death dates, the following conventions will be used for imputing partial dates:

- If only the day of the month is missing, the 1st of the month will be used to replace the missing day. The imputed date will be compared to the last known date alive and the maximum will be considered as the death date.
- If the month or the year is missing, the death date will be imputed as the last known date alive.
- If the date is completely missing but the reason for death is present the death date will be imputed as the last known date alive.

For date of progression, the following conventions will be used for imputing partial dates:

- If only the day of the month is missing, the 1st of the month will be used to replace the missing day*.
- If the day and month are missing or a date is completely missing, it will be considered as missing.

*In cases where the date of death is present and complete, the imputed progression date will be compared to the date of death. The minimum of the imputed progression date and date of death will be considered as the date of progression.

For other partial/missing dates not covered by Core Safety SAP, the following conventions may be used:

- If only the day of the month is missing, the 15th of the month will be used to replace the missing day.
- If both the day and the month are missing, “July 1” will be used to replace the missing information.
- If a date is completely missing, it will be considered as missing.

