4.2.1 Objective Response Rate

The first secondary endpoint is ORR in Arms A and B as determined by investigators. The ORR is defined as the number of subjects with a BOR of CR or PR divided by the number of treated subjects for each treatment group. The BOR is defined as the best response designation, as determined by the investigator, recorded between the date of randomization and the date of objectively documented progression per RECIST 1.1 or the date of subsequent anti-cancer therapy, whichever occurs first. For subjects without documented progression or subsequent therapy, all available response designations will contribute to the BOR assessment. For subjects who continue treatment beyond progression, the BOR will be determined based on response designations up to the time of initial RECIST 1.1 progression.

[figure not shown]

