4.2.2 Progression Free Survival

The second secondary endpoint is PFS in Arms A and B. PFS is defined as the time from the date of randomization to the first date of documented progression, as determined by the investigator per RECIST 1.1, or death due to any cause, whichever occurs first. Clinical deterioration in the absence of progression per RECIST 1.1 is not considered progression for the purpose of determining PFS. Subjects who die without a reported progression will be considered to have progressed on the date of their death. Subjects who did not progress or die will be censored on the date of their last evaluable tumor assessment. Subjects who did not have any on study tumor assessments and did not die will be censored on their date of randomization. Subjects who started any subsequent anti-cancer therapy, including tumor directed radiotherapy and tumor directed surgery, without a prior reported progression will be censored on the date of their last evaluable tumor assessment prior to the initiation of the subsequent anti-cancer therapy.

The progression free survival rate at time T is defined as the probability that a subject has not progressed and is alive at time T following randomization.

Further explanation for various censoring scenarios for the definition of PFS are presented in [Figure 4.2.2-1](#)

Figure 4.2.2-1: Graphic Display of PFS Definition

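### SAP section 8 can date a death in a year the record rules out, and its residual partial-date convention, if it governs subsequent therapy, can place therapy before a known progression

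*SAP*

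**What the plan says.** SAP section 8 (Conventions) refers to the Core Safety SAP and then gives three sets of rules.

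- **Death.** If only the day is missing, the date is the later of the 1st of the month and the last known alive date. Otherwise: "If the month or the year is missing, the death date will be imputed as the last known date alive". A recorded year plays no part.
- **Progression.** If only the day is missing, the date is the 1st of the month, brought back to a complete death date where that is earlier.
- **Everything else.** "For other partial/missing dates not covered by Core Safety SAP, the following conventions may be used". The two conventions are "If only the day of the month is missing, the 15th of the month will be used to replace the missing day" and "If both the day and the month are missing, “July 1” will be used to replace the missing information". Neither is compared with any other date.

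No rule specific to the start of subsequent therapy appears in the supplied text. Two endpoints use that date. Under SAP 4.2.2, subjects who start such therapy (tumor-directed radiotherapy and surgery included) "without a prior reported progression will be censored on the date of their last evaluable tumor assessment prior to the initiation" of that therapy. Under SAP 4.2.1, the best-response window closes at documented progression or "the date of subsequent anti-cancer therapy, whichever occurs first".

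**The concern.** An imputed date should not contradict what the record already establishes. Two rules allow this.

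The death rule discards a known year whenever the month is missing. Every such death goes to the last contact, so OS is shortened, and so is PFS for a death without progression.

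In the PFS definition, the order of therapy and progression decides between event and censoring. A mid-month or mid-year date with no check against progression can reverse that order, and the subject is then censored because of the progression that should have counted.

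Partial dates are foreseeable. Off treatment, survival contacts occur every 3 months by visit or phone and also collect subsequent therapy (Protocol 8.3.2 and Table 5.1-4). For subjects lost to follow-up, vital status may come from public sources (Protocol 3.6.2). PFS, ORR and OS carry the similar-efficacy half of the research hypothesis (Protocol 1.2 and 8.3.2).

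**Working it through.** The plan gives no figure on this point to reproduce. The check applies the stated rules to dates. All calendar dates below are assumed for illustration.

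**1. Death with year known, month missing**

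Imputed date = last known alive (LKA). Earliest date the record allows = 1 January of the recorded year. Minimum error = 1 January − LKA. For a death recorded only as 2017:

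| LKA | Imputed death | Minimum error |
|---|---|---|
| 5 Oct 2016 | 5 Oct 2016 | 88 days |
| 20 Nov 2016 | 20 Nov 2016 | 42 days |
| 20 Dec 2016 | 20 Dec 2016 | 12 days |

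In each row the death falls in 2016, which the record excludes. With contacts every 3 months, gaps of this length are plausible. For LKA 20 November, a true death on 31 December 2017 would be dated 42 + 364 = 406 days early. Using the later of LKA and 1 January 2017 removes the minimum error and leaves at most 364 days.

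**2. Therapy with day missing, same month as progression**

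Scan schedule (Protocol 8.3.2): week 12, then every 8 weeks in the first 12 months. With randomization on 1 June 2016, scans fall on 24 August, 19 October, 14 December and 8 February. Therapy is recorded in the month of progression (PD), day unknown, so it is imputed to the 15th.

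| PD | Imputed therapy | PFS under SAP 4.2.2 | PFS with therapy at the later of the 15th and PD + 1 day |
|---|---|---|---|
| 24 Aug 2016 | 15 Aug | censored, day 0 | event, day 84 |
| 19 Oct 2016 | 15 Oct | censored, day 84 | event, day 140 |
| 14 Dec 2016 | 15 Dec | event, day 196 | event, day 196 |
| 8 Feb 2017 | 15 Feb | event, day 252 | event, day 252 |

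The order inverts exactly when progression falls after the 15th and therapy is recorded in the same month. If only the year is known, 1 July 2016 also precedes 24 August 2016 and gives censoring at day 0.

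In the first row the best-response window closes before the PD scan, so the subject moves from progressive disease to having no assessment in the window. Neither is a response and the ORR denominator is all treated subjects, so ORR does not change there. ORR is exposed only if a first response lies between the imputed and the true therapy date.

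**3. How often the order is wrong, given a day-missing therapy date**

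Let PD fall on each day d of 2016 with equal weight, and let therapy start g days away, g uniform on 1 to G.

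- Therapy truly after PD: share with the 15th of the month of (d + g) earlier than d (event becomes censoring).
- Therapy truly before PD: share with the 15th of the month of (d − g) later than d (censoring becomes event).

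| G (days) | Event → censoring | Censoring → event |
|---|---|---|
| 14 | 26.2% | 21.3% |
| 28 | 13.2% | 10.7% |
| 42 | 8.8% | 7.1% |
| 60 | 6.2% | 5.0% |

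Each column is conditional on the true order it describes. How often each order occurs is not known.

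**The case against.** The strongest reply concerns the therapy date. Section 8 defers to the Core Safety SAP, which is not among the supplied documents, and the 15th and 1 July apply only to what it leaves uncovered, and then only as something that may be used. Its silence on therapy dates cannot be assumed. This stands, so that half of the point is conditional. It does not touch the death rule, which is written out in full.

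Four stronger readings are tempting, and the documents do not support them.

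- A reader might infer that section 8 ignores known dates throughout. It does not: a day-missing death is bounded by last known alive, and a day-missing progression by a complete death date. These bounds show that the authors accept the principle.
- A reader might infer that the therapy error runs one way. The second column of the last table shows the reverse error at a similar conditional rate.
- A reader might want a count of lost PFS events. The documents give neither the number of progressors nor the number of partial dates, so any count would be invented. The rules are also identical in both arms, and no between-arm distortion has been shown.
- A reader might extend the point to a progression imputed before a response in the same month. That needs two scans in one calendar month, whereas scheduled scans are 8 weeks apart with windows of ±1 week, so at least about 6 weeks. Only an unscheduled scan could cause it.

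The secondary analyses are also descriptive, without Type I error control (SAP 7.1), and OS carries no p-value (SAP 7.5.3).

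**Conclusion.** The point holds in two parts of unequal firmness.

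- **Death rule: certain from the wording.** A known year is discarded when the month is missing. The error is always towards an earlier death, by at least the time from last known alive to 1 January whenever the recorded year is later than that contact (12 to 88 days in the examples).
- **Therapy rule: conditional.** It holds only if the Core Safety SAP does not cover subsequent-therapy dates and the optional convention is used. Then about 13% of day-missing records with therapy truly 1 to 28 days after progression would turn a PFS event into a censoring. The share falls to 6% for gaps up to 60 days. These percentages assume progressions spread evenly over the calendar and uniform gaps.

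The overall effect cannot be sized, because the number of partial dates is unknown. It is confined to the descriptive PFS, ORR and OS analyses. The drug-related Grade 3–5 AE endpoint, its CMH test and the sample size are unaffected. This is a low-consequence defect that is worth correcting because the correction is nearly free.

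**What to change.** In SAP section 8:

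(a) For a death with a recorded year and missing month, use the later of the last known alive date and 1 January of that year.

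(b) For a subsequent-therapy start with only the day missing, where a RECIST progression is documented in that same month, use the later of the 15th and the day after progression, unless the record shows that therapy came first. If progression is on the last day of the month, state that the progression date is used and counts as prior progression, so that the imputed date stays in the recorded month. If the Core Safety SAP already has a rule, a cross-reference replaces this item.

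(c) List every imputed death and therapy date, including therapy starts with only the year known. Item (b) does not reorder those, because a year says too little about sequence.

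A floor at the last study-drug dose should not be added for therapy dates. SAP 4.2.2 counts tumor-directed radiotherapy and surgery as subsequent therapy, and SAP 7.2.2 anticipates anti-cancer therapy during study treatment.

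The cost is a few sentences and a few lines of code. The downside of (b) is that a subject who truly switched just before progression in that month is kept as an event. In a 30-day month there are 30 × 29 / 2 = 435 ordered day pairs. The present rule misorders 105 of them (24%) when progression came first, and also 105 when therapy came first (a tie on the 15th counted as an event). Item (b) gives 0% and 100%. With all pairs equally likely, (b) is therefore the better default when progression came first in more than about 76% of such cases. That is why it needs the exception for contrary evidence and the listing.

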9 CONTENT OF REPORTS

All analyses described in this SAP will be included in the Clinical Study Report(s) except where otherwise noted. Refer to the Data Presentation Plan for mock-ups of all tables and listings.
